12. ASSESSMENT OF SAFETY

12.1. Parameters

- Discomfort
- History
- Habitual visual acuity
- Biomicroscopy
- Corneal and conjunctival staining

12.2. Methods

Discomfort will be assessed using questionnaires and the Participant History File at all scheduled visits.

History (including medical and general health) will be recorded on the Participant History File at all visits.

Ocular examination using slit-lamp biomicroscopy will be carried out at baseline and at every visit. Ocular redness (bulbar) and corneal and conjunctival staining will be assessed and recorded using the CCLRU (Appendix II) and CIBA grading scales (Appendix III).

An optometrist will be available for the duration of the study. Participants will be advised to contact the optometrist immediately of any unusual event e.g. unusual redness, pain, irritation, etc. At the clinic, the optometrist will briefly assess the eye on a slit-lamp under low illumination to ascertain the nature of the condition, if any. If an adverse event occurs, the appropriate procedures will be conducted, including referral for medical treatment, if necessary. Any adverse events will be followed until complete resolution to the reasonable satisfaction of the participant and the investigator.

12.3. Definitions

12.3.1. Adverse Events

The principal investigator, or designated personnel determined to be medically qualified by the principal investigator, will question the subject about adverse events. All adverse events will be documented.

12.3.2. Serious Adverse Events

Any adverse medical occurrence that:

- led to death
- led to a serious deterioration in health of a Participant user or other
This would include:
 - a life threatening illness or injury
 - a permanent impairment of body function or permanent damage to a body structure
 - a condition requiring hospitalisation or increased length of existing hospitalisation
 - a condition requiring unnecessary medical or surgical intervention
 - foetal distress, foetal death or a congenital abnormality/birth defect
- might have led to death or a serious deterioration in health had suitable action or intervention not taken place.

12.4. Reporting

In the event of persistent irritation, redness, reduced visual acuity or any other unusual signs or symptoms, the participants will be advised to immediately cease use of the study eye drops and contact the clinic.

Non-serious adverse events should be recorded as part of Good Clinical Practice.

All Serious Adverse Events (SAEs) will be reported to the Co-Sponsor ([REDACTED]) within 24 hours of first knowledge of the event, even if the information is incomplete, using the SAE report form. This procedure is required regardless as to the causal relationship to the study eye drops and also relates to SAEs which are spontaneously reported to investigators from patients taking [REDACTED] products which are not being investigated as part of the study.

[REDACTED]

[REDACTED]

[REDACTED]

[REDACTED]

[REDACTED]

[REDACTED]

[REDACTED]

[REDACTED]

[REDACTED]

[REDACTED]

SAEs will also be reported to the HREC as per their reporting requirements and to other regulatory authorities as applicable under local regulations. This should be followed by a more detailed written report commenting on potential confounding factors, results of investigations, treatment required and outcome. The Sponsor

and the Principal Investigator should review the events in conjunction with the known information about the device, and make a determination as to whether the event is device-related or not.

The investigator agrees to provide written notice to [REDACTED] of any SAEs before publishing any such findings.

All other adverse events should be reported to the Sponsor no later than 10 days after the event.

12.4.1. Foreseeable Adverse Events

Risks associated with the use of the study products are likely to be allergic in nature and include:

- Eye irritation (<1%)
- Eye itching (<1%)
- Eye/eyelid swelling (<1%)
- Eye redness (<1%)

12.5. Follow-up

Participants who experience an adverse response during the course of the trial will be followed up until the condition resolves or the participant is referred to another practitioner. **Permanent discontinuation:** will occur when, in the optometrist’s opinion (or ophthalmologist’s, if participant has been referred), continued use of the study eye drops will be detrimental to ocular health.

13. STATISTICS

13.1. Description

Data stored in relational databases will be imported into SPSS software for statistical purposes. Statistical analysis will initially be reported in Excel. The study may employ at least one interim analysis. Data will be investigated for quality using range checks and frequency distribution. Underlying distributions of variables will be tested. In general, variables measured on an interval scale with a sufficiently large sample size will be considered to follow a normal distribution. Details of statistical analysis are described in Section 13.1.3.

13.1.1. Number of Participants

Up to 40 participants will be recruited (approx. 20 EDE and 20 non-EDE subjects). This sample size was calculated on the basis of detecting a difference in: tear evaporation rate between the eye drops of 36 gm²/h where the expected standard deviation of the measurement is 50 gm²/h, assuming an estimate of type 1 error $\alpha = 0.05$ and power of 80% for a two tailed test.

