
Study Endpoints
	
The primary endpoint is a measurable difference in tear evaporation rate between the eye drops after initial application (15 min) and/or after 1 hour and/or 4 hours of application and/or after 4 weeks of daily use.
 
The secondary endpoints are (i) a measurable difference in TBUT between the

	
eye drops after initial application (15 min) and/or after 1 hour and/or 4 hours of application and/or after 4 weeks of daily use and (ii) a measurable difference in symptom improvement between the eye drops after initial application (15 min) and after 4 weeks of daily use.

Statistical Considerations
	
Paired t-tests, repeated measures ANOVA or linear mixed model analysis using Bonferroni adjustment for multiple comparisons and p value set at $p < 0.05$. Mann Whitney U test will be used to compare tear film lipidome between the eye drops.

IRB Status & Details
	
This clinical research study requires approval from the Human Research Ethics Committee at the University of New South Wales prior to study initiation, any advertising, and participant enrolment.
 
 ○ HREC meetings held monthly ○ Lead time for new applications: approx. 2 months

Dissemination of Results
	
 ○ Publication in peer-reviewed journals ○ Presentation at International conferences

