5. STUDY OBJECTIVES AND CLINICAL HYPOTHESIS

5.1. *Study Objective*

The objective of this study is to measure tear film evaporation rate, tear lipid profile via interferometry and tear lipid components with the use of the emulsion OM3 Tear eye drops, compared to two comparators (Optive Advanced Unit Dose and Optive Unit Dose) in subjects with EDE and those without (non-EDE)

5.2. *Clinical Hypothesis*

Tear evaporation rate as measured with the Vapometer is better (i.e. lower) with the emulsion OM3 Tear formulation compared to at least one of the two comparators at one or more of the post eye drop instillation time-points.

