6. STUDY DESIGN

This study is a single centre, double-masked, randomized, 3-arm comparison of emulsion OM3 eye drops compared to two comparators. All study subjects will attend a Screening visit and receive REFRESH PLUS® for 2 weeks during a run-in period prior to randomization. Subjects will be randomized as to the order of allocation to use the OM3 Tear eye drop and the two comparators. For each arm of the study, assessments will be conducted prior to eye drop instillation and 15 min, 1 hour and 4 hours post-instillation. Subjects will then be dispensed with the randomized study eye drop and instructed to instill 1 to 2 drops of their assigned study product in each eye, as needed, but at least twice daily, for 4 weeks. Subjects will attend a 4 week visit assessment and then undergo a minimum 2 week wash-out period using run-in product REFRESH PLUS® before returning to complete the next arm of the study. These procedures will be repeated until the subjects have completed all 3 arms of the study.

The primary endpoint is a measurable difference in tear evaporation rate between the eye drops after initial application (15 min) and/or after 1 hour and/or 4 hours of application and/or after 4 weeks of daily use.

All proposed procedures conform to the NHMRC Statement on Human Experimentation.

Participants are considered enrolled when they have signed the informed consent form and are regarded as part of the clinical trial population.

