6.2. Primary Endpoint

The primary endpoint is a measurable difference in tear evaporation rate (Vapometer) between the eye drops after initial application (15 min) and/or after 1 hour and/or 4 hours of application and/or after 4 weeks of daily use.

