13.1.3. Analysis

Participants who have commenced the study treatment will be included in the analysis dataset. Reasons and frequency distribution of participants discontinued at the Screening visit will be reported. The analysis of efficacy variables such as subjective ratings will employ only scheduled and evaluable visits. The analysis of safety variables such as adverse responses will include all visits, including all unscheduled visits.

Data will be summarised as means \pm standard deviations for variables measured on an interval scale and median \pm inter-quartile range for ordinal variables. Statistical tests will be employed to determine significant differences between between visits and $p \leq 0.05$ will be considered statistically significant. . Multiple comparisons will be adjusted using Bonferroni's correction. Commonly used tests of significance at each visit may include paired t-tests and group t-test for parametric data and Wilcoxon sign rank test and rank sum test for non-parametric data or repeated measures Analysis of Variance (ANOVA) for parametric data to determine differences between within-subject factors. Ranked variables will be analysed non-parametrically using Friedman's analysis of variance or Wilcoxon Signed Rank test to determine differences. Paired categorical variables will be compared using McNemar's test and grouped categorical variables will be analysed using Chi-Square tests. Mann Whitney U test will be used to compare tear film lipidome between the eye drops.

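### The primary claim can be met by any of several contrasts, the required Bonferroni correction has no defined family, and the stated 80% power is not at the alpha of the corrected test

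*Combined protocol and SAP*

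**What the plan says.** **What counts as success.** The clinical hypothesis (5.2) is that tear evaporation rate is lower with OM3 "compared to at least one of the two comparators at one or more of the post eye drop instillation time-points". The primary endpoint (6.2, repeated in the synopsis and section 6) is any measurable difference among the drops, with the times given as "after initial application (15 min) and/or after 1 hour and/or 4 hours of application and/or after 4 weeks of daily use". The hypothesis names OM3 and gives a direction. The endpoint does neither.

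**Multiplicity rule.** The synopsis offers paired t-tests, repeated measures ANOVA or "linear mixed model analysis using Bonferroni adjustment for multiple comparisons". Section 13.1.3 says "Multiple comparisons will be adjusted using Bonferroni's correction", and its next sentence begins "Commonly used tests of significance at each visit may include paired t-tests and group t-test". Neither place says which comparisons form the family or gives a divisor. Section 13.1.2 keeps a 5% threshold, and 13.1 allows at least one interim analysis without an alpha rule.

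**Sample size.** Section 13.1.1 plans up to 40 participants (about 20 EDE and 20 non-EDE) to detect a difference of 36 where "the expected standard deviation of the measurement is 50", at type 1 error 0.05 and "power of 80% for a two tailed test". Alpha is not divided. The section does not say whether 50 is the SD of one measurement or of a within-participant difference.

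**Visits.** The synopsis visit schedule has a 1-hour assessment for each drop. Tables 4 and 5 have none. The 4-hour visit is optional in both.

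**The concern.** A claim that can be met in several ways needs a correction covering all of those ways. A Bonferroni rule has no definite effect until its divisor is fixed. Divisors of 3, 8 and 12 all fit the present text, and the choice could be made after the data are seen. The smallest of these, the three drop pairs within a visit, leaves the four times uncorrected, yet success at any one of them is enough.

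The power statement has a matching gap. It describes one test at 0.05, while the synopsis and 13.1.3 require corrected tests. At stake are whether a positive primary result can be defended at its nominal error rate, and whether the 80% describes the analysis that will be run.

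**Working it through.** **1. Counting contrasts.**
- Hypothesis (5.2): 2 comparators × 4 times = 8. Without the 1-hour visit, 2 × 3 = 6.
- Endpoint (6.2), any drop pair: 3 pairs × 4 times = 12. Without the 1-hour visit, 3 × 3 = 9.

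**2. The plan's own sample size.** The design is a three-period crossover, so contrasts are paired. Two-sided power is P(|T| > t(1 − α/2, n − 1)), where T is noncentral t with noncentrality 36√n / SD of the difference. At undivided α = 0.05:
- SD of difference 50: n = 18 gives 82.1% (17 gives 79.6%); n = 40 gives 99.3%.
- SD of difference 70.7 (50 as a single-measurement SD, correlation 0): 33 are needed; n = 40 gives 88.1%.

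Neither reading returns 40 exactly. A total of 40 is more than enough for one unadjusted contrast on both.

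**3. False positives if Bonferroni is applied within visit only.** Each test is run two-sided at 0.05/3 = 0.0167, or 0.00833 in one direction. Adding these gives upper bounds that need no correlation assumption:
- OM3 lower: 8 × 0.00833 = 6.7% (four times); 6 × 0.00833 = 5.0% (three times).
- Any drop pair, either direction: 12 × 0.0167 = 20%; 9 × 0.0167 = 15%.

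Simulation under no difference (40,000 trials, all 40 analysed, three drops, four times) allows for shared data. The between-time correlation is an assumption, as the documents give none:

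| Between-time correlation | 0 | 0.3 | 0.5 | 0.7 |
|---|---|---|---|---|
| OM3 lower (nominal 2.5%) | 6.1% | 5.8% | 5.4% | 4.4% |
| Any drop pair (nominal 5%) | 16.2% | 15.8% | 14.5% | 12.3% |

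Repeat runs differ by a few tenths of a point (for example 4.6% instead of 4.4%). Over three times the ranges are about 3.7-4.4% (a repeat run gave up to 4.7%) and 10-13%. At correlation 0.9 over four times, OM3 lower falls to about 3-3.5%.

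With Bonferroni over all 8 OM3 contrasts, each test is at 0.05/8 = 0.00625. The simulated two-sided error is then 3.6-4.7%, within the 5% bound.

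**4. Power per contrast at the corrected alpha.** Difference 36, all 40 pooled and evaluable. If 50 is a single-measurement SD, the SD of the difference is 50√(2(1 − ρ)): 59.2 at ρ = 0.3 and 70.7 at ρ = 0, where ρ is the assumed correlation between drops.

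| SD of difference | 6 tests | 8 tests | 12 tests |
|---|---|---|---|
| 50 | 95.6% | 94.5% | 92.6% |
| 59.2 | 85.0% | 82.3% | 78.2% |
| 70.7 | 66.9% | 63.0% | 57.4% |

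**5. Power for the claim in 5.2, which needs only one success.** Least favourable SD (70.7), 40 participants, 8 tests, effect 36, between-time correlation 0.7 to 0:
- OM3 better than both comparators at all four times: 94-99.8%.
- Better than one comparator at all four times: 84-98%.
- Better than both comparators at one time only: about 79%.

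**The case against.** **Bonferroni is already required.** This stands, and a reader who infers that multiplicity was ignored would be wrong. Error rates for wholly uncorrected testing do not describe this plan. The phrase about tests at each visit belongs to a sentence listing test types and does not define a family. Within-visit correction is therefore a reading that the text permits, not one that it prescribes. What remains is that nothing excludes it.

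**The 12-16% figure is not the error of the hypothesis.** This also stands. It counts differences between the two comparators and results where OM3 is worse. For the directional claim in 5.2 the matching range is 4.4-6.1% against 2.5%, and less at higher correlation. The larger figure applies only to the non-directional wording in 6.2.

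**The trial may not be short of power.** A reader might infer underpowering from the undivided alpha. The documents do not support that: on two of the three SD readings, per-contrast power at 8 tests exceeds 80%, and the chance of at least one success is higher when OM3 is better in more than one contrast. A reader might also note that n = 18 is close to 20 and infer that each group carries its own primary test. No passage says so.

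**The interim analysis may have no efficacy purpose.** Section 13.1 gives neither purpose nor timing, so no inflation can be attributed to it. The only fair request is for clarification.

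**Conclusion.** The point holds as a defect of specification that should be fixed. From the text alone: several contrasts can each satisfy the primary claim, the required Bonferroni correction has no family, and the 80% is calculated at an alpha that the corrected tests will not use.

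The size depends on assumptions. If correction is made within visit only, the false-positive chance over four times is about 4.4-6.1% for OM3 lower (nominal 2.5%) and 12-16% for any difference between drops (nominal 5%). These ranges assume 40 analysed participants and between-time correlation 0.7 to 0. Correction over every primary contrast removes the excess.

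Whether 80% survives correction for a named contrast depends on which SD the 50 is and how many participants are evaluable; 13.1.1 states neither. The power figures assume no losses, although the 4-hour visit is optional and participants discontinued for an adverse response are not replaced (7.3.4). Confidence is high in the gap in the text and lower in any single figure.

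**What to change.** 1. In 13.1.3 and the synopsis, state that the primary tests are OM3 versus each comparator, two-sided, with success only if OM3 is lower, and that Bonferroni or Holm covers every primary contrast and time point. Naming one primary time that all participants attend, with 2 contrasts, is an alternative. It is optional because it demotes the other times in a study designed to follow the effect over time.
2. In 13.1.1, state whether 50 is the SD of the paired difference or of a single measurement (with the correlation, if the latter), and restate power at the adjusted alpha for the pooled population. If EDE and non-EDE are tested separately for the primary claim, count both in the family.
3. Reconcile the 1-hour visit between the synopsis and endpoint text and Tables 4 and 5, so that the divisor is fixed (8 or 6 for the OM3 contrasts).
4. In 13.1, state that any interim analysis makes no efficacy claim, or give the alpha allocated to it.

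The cost is wording in the synopsis, 13.1, 13.1.1 and 13.1.3, plus the visit reconciliation. The downside is that the stated power becomes less favourable. No extra enrolment is proposed.

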13.1.2. Significance

A p-value less than or equal to 5% will be considered to be statistically significant.

13.1.3. Analysis

Participants who have commenced the study treatment will be included in the analysis dataset. Reasons and frequency distribution of participants discontinued at the Screening visit will be reported. The analysis of efficacy variables such as subjective ratings will employ only scheduled and evaluable visits. The analysis of safety variables such as adverse responses will include all visits, including all unscheduled visits.

Data will be summarised as means \pm standard deviations for variables measured on an interval scale and median \pm inter-quartile range for ordinal variables. Statistical tests will be employed to determine significant differences between between visits and $p \leq 0.05$ will be considered statistically significant. . Multiple comparisons will be adjusted using Bonferroni's correction. Commonly used tests of significance at each visit may include paired t-tests and group t-test for parametric data and Wilcoxon sign rank test and rank sum test for non-parametric data or repeated measures Analysis of Variance (ANOVA) for parametric data to determine differences between within-subject factors. Ranked variables will be analysed non-parametrically using Friedman's analysis of variance or Wilcoxon Signed Rank test to determine differences. Paired categorical variables will be compared using McNemar's test and grouped categorical variables will be analysed using Chi-Square tests. Mann Whitney U test will be used to compare tear film lipidome between the eye drops.

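### Section 13.1.3 names visits, not eye drops, as what is compared, so the plan permits the between-drop test of the primary endpoint but does not specify it

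*Combined protocol and SAP*

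**What the plan says.** Section 13.1.3 describes the comparison as follows: "Statistical tests will be employed to determine significant differences between between visits". It then offers a menu: "Commonly used tests of significance at each visit may include paired t-tests and group t-test for parametric data", with signed rank and rank sum tests as the non-parametric counterparts, or "repeated measures Analysis of Variance (ANOVA) for parametric data to determine differences between within-subject factors". Those factors are not named. The only sentence there that names the drops concerns a different outcome: "Mann Whitney U test will be used to compare tear film lipidome between the eye drops". The synopsis (Statistical Considerations) adds a linear mixed model as an option, also without naming factors.

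Elsewhere the question is about drops. Section 6.2 defines the primary endpoint as "a measurable difference in tear evaporation rate (Vapometer) between the eye drops", at 15 minutes, 1 hour, 4 hours or 4 weeks. Section 5.2 expects a lower rate with OM3 "compared to at least one of the two comparators at one or more of the post eye drop instillation time-points". Section 13.1.1 sizes the study on a between-drop difference of 36 with an SD of 50. Section 6 sets the design: "Subjects will be randomized as to the order of allocation to use the OM3 Tear eye drop and the two comparators".

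**The concern.** In this design a visit identifies a period and a time. It does not identify a product. Eye Drop #1, #2 and #3 in the schedules mark order of use, so each period holds a mixture of all three products. A contrast of visits across periods therefore measures period, and a contrast of visits inside one period measures change on a single drop. Neither is OM3 minus a comparator.

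The text leaves at least four analyses open for tear evaporation rate: period against period, change within a drop, an unpaired comparison of people on different drops, and a paired comparison of drops. They answer different questions and differ in precision. If the choice is made once data are in hand, the primary analysis has not been prespecified. Section 6.1.2 adds to the risk of an unpaired analysis, because it describes assignment at Visit 2 to one of three treatments, which on its own reads like a parallel-group trial.

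**Working it through.** **1. The plan's own sample size.** Inputs from Section 13.1.1: difference 36, SD 50, two-sided alpha 0.05, power 80%.

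- Paired test, taking 50 as the SD of the difference: n = (50 × (1.960 + 0.842) / 36)² = 3.89² = 15.1, so 16. With the noncentral t distribution, 18. This is within two of the approximately 20 per group.
- If 50 is the SD of one measurement, the SD of the difference is 50 × √(2(1 − ρ)). For ρ = 0, 0.3, 0.5 and 0.7 that is 70.7, 59.2, 50 and 38.7, and n is 33, 24, 18 and 12.
- Two independent groups: 2 × 15.1 = 30.3, so 31 per group (32 with t). This matches neither 20 nor 40.

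The figure that reproduces is a paired contrast between drops. The plan does not say which SD is meant.

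**2. What a visit contrast estimates.** Write each observation as participant + period + drop + error. Assume the orders are balanced; the plan says only that order is randomised. OM3 is then used by one third of participants in each period. If OM3 is 36 lower than both comparators, it contributes −36 × 1/3 = −12 to the mean of every period. The difference between two periods is then (−12) − (−12) = 0 plus any period effect, so the drop effect cancels. Within one period, before against after, or 15 minutes against 4 weeks, the drop is constant and no contrast between drops exists.

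**3. Visit is itself ambiguous.** The synopsis schedule numbers visits 1 to 7, so Visit 3 is the 4-week visit on the first drop. Tables 4 and 5 use 2a to 4c, so Visit 3a starts the second drop. Visit 2 against Visit 3 is a within-drop comparison in one scheme and a cross-period comparison in the other.

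**4. What is lost if the group t-test is used between drops.** At one visit number, 40 / 3 is about 13 people per drop, and 20 / 3 is about 7 within EDE or non-EDE. Take 50 as the SD of one measurement, with alpha 0.05 and no Bonferroni adjustment.

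- 13 v 13: noncentrality 36 / (50 × √(2/13)) = 36 / 19.6 = 1.84, 24 df, power 42%.
- 7 v 7: 36 / (50 × √(2/7)) = 36 / 26.7 = 1.35, 12 df, power 24%.
- Paired: noncentrality 36 × √n / SD of the difference.

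| ρ | SD of difference | Paired power, n = 20 | Paired power, n = 40 |
|---|---|---|---|
| 0 | 70.7 | 58% | 88% |
| 0.3 | 59.2 | 73% | 96% |
| 0.5 | 50 | 86% | 99% |
| 0.7 | 38.7 | 98% | >99.9% |

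**5. The lipidome test.** Mann Whitney assumes independent samples. Every participant is planned to use all three drops, so the one test that Section 13.1.3 assigns to drops ignores the pairing.

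**The case against.** The strongest reply is that the plan is under-specified but does not prescribe a wrong analysis. The key sentence is visibly garbled, with a doubled word, and is probably a drafting slip. In a three-drop crossover, eye drop is an obvious within-subject factor for the ANOVA. The synopsis methods are not tied to visits, and the hypothesis, endpoint and sample size all state the between-drop contrast. A careful analyst would probably find it. This stands, and it limits the finding to wording and specification. It does not remove it: the analysis section should not depend on readers setting aside its own words.

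Three stronger readings are tempting, and the documents do not support them.

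- A reader might infer that no test done at each visit compares drops. That phrase can mean at each post-instillation time point, paired across drops. A group test at one visit number does compare drops, inefficiently, or it can compare EDE with non-EDE.
- A reader might take the cancellation in step 2 as the trial's expected chance of missing a real effect. It shows only what happens if treatment labels are ignored, and no section says that they will be.
- A reader might expect OM3 to be declared better because its change from pre-instillation is significant while a comparator's is not. The plan nowhere proposes that.

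Likewise, Section 13.1.3 does not assign the group t-test or rank sum test to drops. The power loss in step 4 arises only if they are used that way.

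**Conclusion.** The point holds as a mismatch of wording and specification that should be fixed before analysis. Taken literally, the stated comparison does not estimate the primary endpoint. The right test is available under other wording in the plan, but it is not named, and no eye-drop, period or sequence term appears for tear evaporation rate.

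The sample size stands. It reproduces at 18 against about 20 per group, provided that 50 is the SD of the paired difference (equivalently, a single-measurement SD of 50 with correlation 0.5). The avoidable loss, if an unpaired test were used between drops at one visit, is from 88% or more to about 42% power with all 40 participants. Within one group of 20 it is from between 58% and 98% to about 24%. These figures assume a single-measurement SD of 50, correlation of 0 to 0.7, equal numbers per drop, no missing data and no multiplicity adjustment. The documents give no correlation. It would be wrong to conclude that the trial will fail to test its endpoint.

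**What to change.** In Section 13.1.3:

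1. Replace the comparison between visits with: *between eye drops at the same post-instillation time point, as the within-participant difference OM3 minus each comparator, with a 95% confidence interval*.
2. Name the analysis for tear evaporation rate: a paired or mixed model with eye drop and period terms. The synopsis already allows a mixed model.
3. Label tests between visits within one drop as descriptive and not part of the primary endpoint.
4. Restrict the group t-test and rank sum test to comparisons of EDE with non-EDE.
5. For lipidome comparisons between drops, replace Mann Whitney with a paired test. The Wilcoxon signed rank test is already on the section's list. Make the same change in the synopsis.

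The cost is a few sentences in Section 13.1.3 and one in the synopsis. Visits, data collection and sample size do not change.
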